Single-shot intrathecal morphine sulfate (ITM) injected while performing a spinal anesthetic for CS has been considered the gold standard for post CS pain. ITM provides analgesia for about 14-36 hours. Variable doses of ITM ranging between 50 – 250 micrograms (μ cg) have been used. Lower doses of ITM results in fewer side effects however present a tradeoff of shorter duration of analgesia.(Sutton and Carvalho 2017a) Side effects of ITM can be treated with effective prophylaxis and treatment medications. Nalbuphine and naloxone are given to treat pruritus. Nausea and vomiting are treated with ondansetron, metoclopramide, promethazine, and propofol. Respiratory depression is seen with higher doses of ITM ($\geq 150 \mu$ cg). Patients, who are obese, have obstructive sleep apnea and are on chronic pain medications or patients with opioid tolerance have a higher incidence of respiratory depression. Respiratory depression is treated with naloxone bolus followed low dose naloxone infusion. This can antagonize opioid effect and result in pain. Patients with pre-eclampsia receive magnesium, which is sedating and can further cause respiratory depression.(Sutton and Carvalho 2017a) The bimodal respiratory depression associated with ITM requires intense monitoring of respiratory status for the first 24 hours and special training for providers caring for these patients.

Eighty-one percent of all women in the US initiate breast-feeding (BF) postpartum. Early BF improves maternal-neonatal bonding. Effective pain control promotes successful BF.

A relative infant dose (RID) expressed as a percentage and is weight adjusted for the neonate (Table 1). It quantifies the amount of neonatal drug exposure relative to the mother’s dose. A value of greater than 10% is considered high. (Sutton and Carvalho 2017b) Highly protein bound drugs like non-steroidal anti-inflammatory drugs (NSAID’s) and local anesthetics (LA) have limited transfer to the neonate.

Acetaminophen provides effective analgesia PP with minimal side effects as a part of the multimodal analgesia plan (MPP). It has an opioid sparing effect of approximately 20%.

Scheduling acetaminophen for 2-3 days post CS has been recommended.(Bollag et al., n.d.)

Ibuprofen has a short half-life. RID is 0.6% in colostrum and <0.38% in mature milk. This is equivalent to 0.2% of the pediatric dose. Scheduled ibuprofen for 2-3 days has also been recommended in addition to scheduled acetaminophen. (Bollag et al., n.d.)

Table 1: Relative infant dose for different medications

Drug	Relative infant dose
Acetaminophen	1.3-6.4
Ibuprofen	0.1-0.7
Ketorolac	0.2-0.4
Celecoxib	0.3
Gabapentin	1.3-6.5
Hydrocodone	1.6-3.7
Oxycodone	1.5-8
Tramadol	2.4-2.9
Fentanyl	0.9-3
Morphine	5.8-10.7

The quadratus lumborum block (QLB) was initially described by R. Blanco.(Blanco, Ansari, and Giris 2015) This block covers not only the somatic innervation of the body wall, but also provides relief of visceral pain. Given its versatility, the quadratus lumborum block has successfully been used in a wide range of procedures including gastrectomies, colectomies, prostatectomies, nephrectomies, cystectomies, cesarean sections and hysterectomies.

There are three types of quadratus lumborum blocks: quadratus lumborum type 1 (QLB1), quadratus lumborum type 2 (QLB2) and trans-muscular quadratus lumborum block (TQLB). For all three blocks, the needle enters the lateral abdomen near the posterior axillary line, below the costal margin and above the iliac crest. In QLB1, the anesthetic agent is injected into the potential space medial to the abdominal wall muscles and lateral to the quadratus lumborum muscle (QL). This block covers the dermatomal

area from T10 to L1, and is typically used for abdominal surgeries being conducted below the umbilicus. In QLB2, the anesthetic agent is injected just posterior to the QL muscle and covers T4 to L1. The QLB2 block effectively blocks the anterior and lateral cutaneous branches of the nerves. It is typically used for abdominal surgery either above or below the umbilicus (any type of operation that requires intrabdominal visceral pain coverage and abdominal wall incisions as high as T6). In TQLB, the anesthetic agent is injected anterior to the QL muscle, between the QL and the psoas major muscles. This block has analogous coverage to the QLB2 block and thus has the same clinical indications as the QLB2 block. However, this block is more difficult to perform than the QLB2 block, and can result in quadriceps weakness due to spread to the lumbar plexus on the anterior surface of the psoas major muscle. (Ueshima, Otake, and Lin 2017)

Early oral intake, mobilization, removal of urinary catheter are all important components of the enhanced recovery after surgery protocol (ERAS). We hypothesize that by performing QL blocks post CS the amount of pain, narcotic consumption will be reduced significantly. Early ambulation will help prevent deep vein thrombosis. Performing QL blocks will also minimize side effects secondary to ITM and will facilitate ERAS and better patient satisfaction scores.

A recent study conducted by Salama et al concluded that QLB (without ITM) provided lower numeric rating scores at rest and during movement when compared to the group that received ITM (without QLB). Time to first morphine dose was also longer in the QLB. This study concluded that a longer duration of analgesia and reduced postoperative morphine consumption was achieved with QLB when compared to ITM.(Salama 2019)

X. Sample size

25 in each group

Total number of enrolled patients: 75

XI. Study population

Inclusion criteria

1. Age greater than 18 years
2. Elective C section via Pfannenstiel incision
3. Living singleton pregnancy
4. Gestation week at least 37 weeks
5. ASA status 1, 2 and 3

6. Primary and secondary C sections

Exclusion criteria

1. Chronic pain
2. Opioid tolerant patients
3. Allergy to drugs used in the study.
4. Cognitive dysfunction
5. BMI > 40
6. Coagulation disorder
7. Local infection
8. Inability to tolerate oral medication
9. Previous intra-abdominal surgery
10. Patients who will receive a combined spinal epidural for their C section
11. Local anesthetics injected at any other fascial plane except the QLB plane (for e.g.- local wound infiltration by surgeon)
12. Patients who received sedation or general anesthesia during their CS (midazolam, ketamine, fentanyl, propofol, hydromorphone)

Voluntary patient withdrawal from the study- patient has right to withdraw at any point during the study period

Withdrawal in case of unexpected events- This will be determined by the investigators.

XII. Primary objective

Primary objective of the study is to compare opioid consumption in morphine equivalents between the groups that received postoperative analgesia with intrathecal morphine versus US guided QL blocks versus US guided QL catheters

Our working hypothesis is-

1. Single shot QL block is equivalent to intrathecal morphine with less side effects in providing post-operative pain control for the first 24 hours.

2. Continuous QL catheter is more beneficial than single shot QL block or intrathecal morphine after 24 hours in providing post-operative pain control.
3. Our exploratory hypothesis is that after 48 hours a QL catheter would continue to reduce morphine consumption until 72 hours.

Primary outcome measure

Total narcotic consumption in morphine equivalents (in milligrams) for the first 72 hours after surgery will be calculated. Total narcotic used in the spinal anesthetic will be excluded.

XIII. Secondary objectives

1. Total narcotic usage at 24 and 48 hours will be assessed in morphine equivalents. Intraoperative consumption of opioids will be excluded.
2. Time to first analgesic request
3. Numeric pain score (NPS)- static and dynamic at 6, 12, 24, 48 and 72 hours
4. Pruritus at 24, 48 and 72 hours
5. Nausea at 24, 48 and 72 hours
6. Vomiting at 24, 48 and 72 hours
7. Sedation at 24, 48 and 72 hours
8. Patient satisfaction- quality of sleep, ability to ambulate, and ability to breast feed and take care of newborn at 24, 48 and 72 hours

Secondary outcome measures-

1. Total narcotic consumption in morphine equivalents (in milligrams) at 12, 24 and 48 hours will be measured.

Time after CS	Total morphine equivalents (mg)
At 4 hours	
At 6 hours	
At 12 hours	

At 24 hours	
At 72 hours	

2. Time to first analgesic request will be reviewed from the chart
3. Our research personnel will use NPS. This will be assessed at 6, 12, 24, 48 and 72 hours. NPS is a 11-point scale as shown below. The study patient will verbally select a numerical value that best corresponds with the pain the patient is experiencing at that point. This data will be statistically analyzed. Static and dynamic pain scores will be assessed. Dynamic pain scores will be assessed by asking the patient to sit up in bed from supine to sitting at 6 hours. This will be repeated at 12, 24, 48 and 72 hours however if patient is ambulating, dynamic pain score during ambulation will be assessed.

No pain

Distressing pain

Worst pain

No pain (0)

Mild pain (1,2,3)

Moderate pain (4,5,6)

Severe pain (7,8,9,10)

Time interval after CS	NPS (static)	NPS (dynamic)
At 6 hours		
At 12 hours		
At 24 hours		
At 48 hours		
At 72 hours		

4. Numeric scale to rate side effects (SE) of pruritus, nausea, vomiting and sedation at 24, 48 and 72 hours; 0- no side effects 10- extremely severe side effect possible. This numeric scale is a 11-point scale as shown below. The study patient will verbally select a numerical value that best corresponds with the side effects the patient is experiencing at that point. This data will be statistically analyzed.

No SE

Distressing SE

Worst SE

No SE (0)

Mild SE (1,2,3)

Moderate SE (4,5,6)

Severe SE (7,8,9,10)

Side effects	Scale at 24 hours	Scale at 48 hours	Scale at 72 hours
Pruritus			
Nausea			
Vomiting			
Sedation			

5. Patient satisfaction will be measured on a Likert scale (5 points) at 48 and 72 hours. How satisfied were you with the following?

	Extremely satisfied	Very satisfied	Moderately satisfied	Slightly satisfied	Not satisfied
Quality of sleep					
Ability to ambulate					
Ability to breast feed/ formula feed					
Ability to take care of new born					

XIV. Study drugs

1. Preservative free morphine
2. Normal saline
3. Bupivacaine hydrochloride 0.25 %
4. Ropivacaine hydrochloride 0.1 % XV.

Study schedule

Expected start date for enrolling patients

Expected end date for enrolling patients

Enrollment period for each patient- 72 hours, earlier if discharged.

XVI. Study design

This is a prospective double-blinded randomized control trial performed at a single institution.

Screened patients meeting inclusion criteria will be randomized into three groups:

Group 1- Spinal anesthesia with ITM + US guided QLB single shot sham block + QLB catheters with no continuous infusion

Group 2- Spinal anesthesia without ITM + US guided QLB single shot with bupivacaine hydrochloride + QLB catheters with no continuous infusion

Group 3- Spinal anesthesia without ITM + US guided QLB single shot with bupivacaine hydrochloride + QLB catheters continuously infusing 0.2% ropivacaine hydrochloride

Placement of spinal anesthesia- This will be performed by the attending anesthesiologist or anesthesiology resident who are providing anesthesia for the patient in the operating room. The anesthesia technique will be standardized. A spinal anesthetic will be performed in the sitting position at the lumbar vertebra level (L) either at L3-L4 or L4-L5 level. All women will receive a spinal anesthetic using 0.75% hyperbaric bupivacaine 912 mg plus fentanyl 20 micrograms plus epinephrine 1:100,000 100 micrograms administered intrathecally. The anesthesiologist caring for the patient will not be blinded. The anesthesiologist caring for the patient will open an opaque envelope handed to him/her by the research personnel. The envelope will clearly state the group the patient is assigned to and if ITM 200 micrograms should be added or excluded from the spinal medication. Spinal block efficacy will be considered successful if a sensory block to pinprick is achieved at a level of thoracic (T) 6 or higher. Anesthesia and surgery will be performed in the usual manner.

Placement of QL blocks- Immediately after wound closure, bilateral QL blocks will be placed by one of the investigators under direct ultrasound guidance (Sonosite X-Porte, Sonosite, Bothell, WA). For the purpose of our study we will be utilizing the QL 2 technique by Blanco to achieve blockade from T7-L1 dermatomes.(Blanco et al. 2016; Blanco, Ansari, and Grgis 2015) The anesthesiologist caring for the patient will open the opaque envelope and prepare the study drug. The study drug will either be a sham 20 ml empty syringe or 0.25% bupivacaine hydrochloride 20 ml each side. The patients will be in the supine position with a small roll of blanket placed under the ipsilateral flank. The abdomen will be cleaned with 2 % chlorhexidine gluconate and 70 % isopropyl alcohol solution (ChloraPrep® One-Step). If the patient has an allergy to any of the contents of

the cleaning solution, 10% Povidone-Iodine solution will be used. The ipsilateral abdomen will be draped with sterile towels. A transverse linear array probe (HFL50 6-15 MHz) placed in a sterile probe cover with an imaging depth of 4-6 cm will be placed at the level of the anterior superior iliac spine and moved cranially until the three abdominal muscles are identified; external oblique (EO), internal oblique (IO), transverse abdominis (TA). The EO muscle will be followed posterior and laterally until its posterior border is visualized. The IO muscle should come into view overlying the QL muscle. The probe will be tilted to identify a bright hyperechoic line that corresponds to the middle layer of the thoraco-lumbar fascia. An 18 G echogenic peripheral nerve block needle (Contiplex® Ultra 360™ continuous nerve block set, B Braun, Bethlehem, PA, USA) will be inserted in plane from anterolateral to posteromedial direction. The optimal point of injection for the QL will be determined by hydro dissection with normal saline. Primary block will be performed depending on the group allocation of the patient. The patient will receive either no drug (Group 1) or bupivacaine hydrochloride (Group 2 and Group 3). QL catheters will be placed as described below. A QL2 block will be performed on the contralateral side in a similar fashion.

Placement of QL catheters- A 20 G peripheral nerve polyamide catheter (Contiplex® Ultra 360™ continuous nerve block set, B Braun, Bethlehem, PA, USA) will be inserted through the 18 G echogenic needle under direct ultrasound visualization. The catheter will be secured using the standard technique employed at our institution. Correct placement of QL catheters will be confirmed by injecting saline under ultrasound guidance. QL catheter will be placed on both sides in a similar fashion. A member of the research team who performed the initial QLB in the operating room will attach a peripheral nerve pump (CADD® Solis ambulatory infusion pump, Minneapolis, MN, USA) to the QL catheter once the patient reaches the post anesthesia care unit (PACU). No infusion will be initiated if the patient is assigned to group 1 (Spinal anesthesia with ITM + US guided QLB single shot sham block + QLB catheters with no continuous infusion) and group 2 (Spinal anesthesia without ITM + US guided QLB single shot with bupivacaine hydrochloride + QLB catheters with no continuous infusion). Infusion of 0.2 % ropivacaine at 10 ml/hour on each side will be initiated if the patient is randomized to group 3 (Spinal anesthesia without ITM + US guided QLB single shot with bupivacaine hydrochloride + QLB catheters infusing 0.2% ropivacaine hydrochloride). A member of our research team who is blinded to the group allocation will manage all peripheral nerve catheters. No extra bolus medication will be given through any of the catheters. We are not initiating any infusion through the peripheral nerve catheters in group 1 and 2 to avoid the possibility of pain due to stretching of muscles and facial planes by normal saline.

All patients will be started on a multimodal pain regimen. They will receive scheduled acetaminophen 1000 mg orally and ibuprofen 600 mg every 6 hours. Oxycodone 2.5 mg-5 mg oral every 4 hours as needed will be added for breakthrough pain. Patients will be

evaluated by the anesthesia pain service for adding a PCA with intravenous hydromorphone if pain not adequately controlled on their regimen.

Our research personnel who will be blinded, will follow up patients for the first 48 hours to collect data listed under primary and secondary objectives. We are not assessing dermatomal levels to determine the spread of local anesthetic as it could possibly result in patients and study personnel knowing which group they fall under and potentially unblinding the study.

XVII. Conduct

1. Screening

Our research team will assess patients for eligibility based on the inclusion criteria. We will obtain informed written consent from all eligible patients. Any member of our research team at any point will obtain this consent during the preoperative period (anesthesia clinic, surgery clinic, preoperative holding area). Patients will be given adequate time to consult with family members and use the internet for additional information. All questions and concerns by the patient will be addressed at this point.

Once a written informed consent is obtained the patient will be educated about the study protocol, NPS assessment, other assessment tools and the use of MMP medications. Baseline pain score will be recorded at this point. A complete preoperative evaluation, physical examination and preoperative testing will be conducted per usual protocol by the anesthesiologist caring for the patient.

Three copies will be made of the written informed consent. Patient will be given a copy of the signed written informed consent. A copy of the consent will be placed in the patient's chart. Our research team will keep one copy of the consent.

2. Enrollment

Patient will be enrolled if all inclusion, exclusion criteria are met and the patient has provided an informed written consent. Our research coordinator will then randomly assign the patient into one of the groups based on the random allocation software.

3. Randomization and allocation concealment

Anesthesiologist in the operating room will not be blinded to the patient's randomization, as they must prepare the spinal with or without intrathecal morphine and the prescribed solution for block placement. Anesthesiologist performing the regional nerve block not be blinded as they will have to perform a

sham QLB or a QLB with the study drug. All other research personnel collecting data or seeing the patient postoperatively will not know what the contents of the spinal medication were, whether or not the QLB contained no drug or bupivacaine, or whether the QLB catheter infusions contain no drug or ropivacaine.

Patient's assigned group will be communicated to the anesthesiologist caring for the patient in an opaque envelope so that no other research personnel are wise to the assignment.

Research personnel responsible for randomizing and assigning group will not be the same personnel as those evaluating the patient or collecting data.

4. Preoperative assessment

A complete pre-operative assessment will be done by the anesthesiologist or resident physician caring for the patient. Our research personnel will only evaluate patient to verify if they meet our inclusion criteria.

5. Follow up

Our research personnel who will be blinded to the study drugs used, will follow up patients.

Following data will be collected from the patient at the following time intervals.

At 6 hours	NPS		
At 12 hours	NPS		
At 24 hours	NPS	NRS for SE	
At 48 hours	NPS	NRS for SE	Likert scale for patient satisfaction

6. Termination of enrollment

Enrollment will be terminated if the following criteria are met-

- i. At the end of the 48-hour period
- ii. Intraoperative complication resulting in post-operative prolonged ventilation
- iii. Failure of neuraxial spinal anesthesia or conversion to general endotracheal anesthesia during the C section

- iv. Pfannenstiel incision converted to any other type of incision during surgery
- v. Patient death within 48 hours
- vi. Termination of study

7. Termination of study

After data collection, analysis and publication of results.

XVIII. Adverse event reporting

All patients will be monitored for adverse events. Adverse events if any will be duly documented in the research file as well as in the patient's medico legal record. All adverse events will be reported to the data safety monitoring board (DSMB). The patient will be informed of all adverse events such as local anesthetic systemic toxicity, local infection, bleeding.

XIX. Sample size and statistical analysis

Size consideration:

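### From 12 h on, dynamic pain is scored on sitting up or on walking depending on whether the patient is walking, so the arms may be compared on different mixes of tasks

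*Combined protocol and SAP*

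**What the plan says.** Section XIII lists the endpoint among the secondary objectives: "Numeric pain score (NPS)- static and dynamic at 6, 12, 24, 48 and 72 hours". Item 3 of the secondary outcome measures defines the provoking movement. For the first assessment: "Dynamic pain scores will be assessed by asking the patient to sit up in bed from supine to sitting at 6 hours". At 12, 24, 48 and 72 h the same movement is repeated, "however if patient is ambulating, dynamic pain score during ambulation will be assessed".

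The data table under item 3 has one static and one dynamic column for each time, with no field for the movement performed. The follow-up table in section XVII, item 5, says only NPS. The statistical analysis plan in section XIX does not mention dynamic pain by name. Its general rule for continuous variables is a two-sample t test between any two groups, or a Wilcoxon rank sum test if the variable is skewed. It provides no stratification, adjustment or sensitivity analysis by task.

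On the expected effect of treatment, the background text just before section X names mobilization as a component of the enhanced recovery (ERAS) pathway and then says: "Performing QL blocks will also minimize side effects secondary to ITM and will facilitate ERAS and better patient satisfaction scores".

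**The concern.** At four of the five assessment times, what is measured depends on something observed after randomisation: whether the patient is walking. If the blocks speed recovery as the protocol hopes, the share of patients scored on walking could differ between arms at the same visit. A difference in mean dynamic NPS would then combine a difference in pain with a difference in what patients were asked to do. Randomisation does not protect against this, because the task is chosen afterwards.

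The error could go either way. Arms with equal pain could appear to differ, or a real difference could be masked. Dynamic NPS is the trial's only measure of pain on movement, and the working hypotheses in section XII are worded in terms of postoperative pain control. The 12 h and 24 h scores fall within the 24-hour window of the first hypothesis, where a masked difference could be read as support for equivalence. Because the form does not capture the task, the problem could not be examined later from the planned data.

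**Working it through.** The plan gives no figure for dynamic pain to reproduce; the calculations in section XIX concern morphine equivalents only. The check is therefore a formula with assumed inputs.

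**Formula.** Let *g* be the average walking-minus-sitting pain difference among patients who are walking, taken as equal in both arms, and let *p*A and *p*B be the shares walking at a visit. Each arm's mean recorded score is its mean sitting-up score plus *g* × *p*. So:

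observed difference (B − A) = true sitting-up difference + *g* × (*p*B − *p*A)

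The last term is the bias. It is zero if *g* = 0 or *p*A = *p*B, and close to zero if nearly everyone, or no one, is walking in every arm.

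**Inputs from the documents.** 25 patients per group (section X); significance at P < 0.05 and two-sample tests (section XIX).

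**Inputs assumed.** *g*, *p*A, *p*B and an NPS standard deviation of 2. None of these is in the documents.

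**Range of the bias.**
- Low end: 1 × (0.60 − 0.40) = 0.2 points.
- High end: 2 × (0.70 − 0.30) = 0.8 points.

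**Effect on the test.** 20,000 simulated two-sample t tests per setting, 25 per arm, two-sided 0.05, no true difference between arms on either task:

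| *g* (points) | 40% vs 60% walking: bias, rejection rate | 30% vs 70% walking: bias, rejection rate |
|---|---|---|
| 0.5 | 0.1, 5.2% | 0.2, 6.2% |
| 1 | 0.2, 6.2% | 0.4, 10.6% |
| 2 | 0.4, 9.5% | 0.8, 24.5% |

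With equal shares walking, the rejection rate is about 5% for every *g*.

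**Masking.** Suppose the better arm truly has 1.5 points less pain on both tasks, walking hurts more than sitting up, and 70% of that arm is walking against 30% of the other.
- *g* = 1: observed difference −1.5 + 1 × 0.4 = −1.1. Simulated power is 46%, against 71% with equal shares (50% in each arm).
- *g* = 2: observed difference −1.5 + 2 × 0.4 = −0.7. Simulated power is 19%, against 64% with equal shares.

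If walking hurts less than sitting up, *g* is negative and the faster-recovering arm is favoured instead.

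**The case against.** The same rule applies in every arm, and the 6 h score uses one task for all. A reader might infer that the arms are simply compared on different tasks. The documents do not support that: only the mix can differ, only from 12 h, and only if walking rates differ by arm at that visit.

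The evidence that treatment affects walking is indirect. The sentence "Early ambulation will help prevent deep vein thrombosis" states a benefit of walking and says nothing about a difference between arms. The satisfaction item ("Patient satisfaction- quality of sleep, ability to ambulate, and ability to breast feed and take care of newborn") records satisfaction with ability to ambulate, not whether the patient is walking. The enhanced recovery sentence is the relevant support, but it sets QL blocks against intrathecal morphine. Groups 2 and 3 both receive a bupivacaine block, so it gives no direct reason to expect different walking rates between those two.

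The size is wholly assumed, and the top of the range needs both extremes together. More extreme inputs, such as 20% against 80% walking with a 2-point task difference, push the simulated false-positive rate to about 50%. Nothing in the documents makes a gap of that size likely, and it should not be used to judge how serious the point is. If walking hurts more, the bias also works against a false claim of benefit for the faster-recovering arm.

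Pain on walking is also a legitimate functional measure. That is a reason to record it, not to merge it with pain on sitting up. One could read the rule as adding a walking score rather than replacing the sitting-up score, but substitution is the natural reading and the form has room for only one dynamic score.

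These arguments limit the point to a conditional one. None supplies a common task or a record of the task performed.

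**Conclusion.** The point holds in conditional form. At 12, 24, 48 and 72 h, a post-randomisation state that the protocol expects QL blocks to influence decides which movement is scored, and neither the form nor the analysis accounts for it. Whether this biases dynamic NPS depends on two quantities the documents do not give: the difference in walking rates between arms and the difference in pain between the tasks. The 0.2-0.8 point range is an illustration under those assumptions, not an estimate, and the direction is unknown. A reader might infer that the trial's main result is at risk. It is not: dynamic NPS is a secondary endpoint, and the limits stated above leave the primary opioid outcome, static NPS, the 6 h dynamic score and the sample size untouched. The change is worth making because it removes a plausible bias cheaply, and because the planned data would not allow a repair afterwards.

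**What to change.** In section XIII, item 3, score the supine-to-sitting movement in every patient at every scheduled pain assessment, and make that score the dynamic NPS used for comparisons between arms. It is already the 6 h task and the task for patients who are not walking. Add two separate items to the form: ambulating (yes/no), and pain on walking for those who are.

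If a common task cannot be adopted, the minimum is to record the task performed and report scores by task. That is weaker, because a comparison within one task still conditions on a post-randomisation state.

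Cost: at each visit, a patient already walking makes one extra supine-to-sitting movement and gives one extra verbal score. The form gains two fields, and no sample size or power figure changes.

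One matter needs separate reconciliation. Section XIII schedules a 72 h score, while the end of section XVI and section XVII, items 5 and 6, stop follow-up at 48 h. The common task should apply at whichever assessments are kept.
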